## **DATA AND SPECIMEN MANAGEMENT:**

### **Statistical analysis:**

The primary endpoints of the study are graft function and subpopulations of T cells, including regulatory T cells and B cell subpopulations as well as immune functions at 3 and 12 months post kidney transplant.

The secondary endpoints of the study include 1) incidence of acute rejection, graft loss, and death at 3 and 12 months post kidney transplant; 2) allograft immunohistopathology profiles at 3 and 12 months post kidney transplant.

We will run univariate and bivariate analyses for all variables prior to our main analyses. We will evaluate continuous variables using t-tests or F-tests and categorical variables using  $\chi^2$ . We will examine data distributions and test all variables for linear relationships or non-linear relationships.

Descriptive statistics (means, standard deviation, frequency) and correlations (both Pearson and Spearman) among variables will be calculated for preliminary data assessment.

Necessary transformation and imputations will be carried out based on the raw data distribution.

As missing data are inevitable in a longitudinal study, we will determine whether missing data are MCAR (data are missing completely at random), MAR (data are missing at random), or NMAR (not missing at random). If missing data are MCAR or MAR, it is likely that the standard multivariate computations using PROC MI (multiple imputations) will not result in biased standard error estimates. However, if missing data are NMAR, we will use the "pattern mixture" approach to compute a weighted average of the parameters that are associated with the missing data to estimate what the data would have been.

For the primary objective, we hypothesize that subjects receiving LCP-Tacrolimus/Envarsus® XR will exhibit significantly greater graft function and lower frequency / abundance of AlloSeq pre-identified donor-reactive T cell clones in the graft, peripheral blood and /or urine at 3 and 12 month post-transplant as compared to the standard of care tacrolimus group. A variety of covariance structures (first order regressive, compound symmetry, Toeplitz, variance components, unstructured) will be carefully examined and compared using the best fitting statistics, such as Akaike's Information (AIC) and Bayesian Information Criteria (BIC). These statistics are likelihood functions and can be compared across models. If, in spite of randomization, distributions of subjects' baseline characteristics are found to be different between the two experimental groups, these variables will be entered as covariates in the statistical analysis.

For the secondary endpoints, we will use logistic regression, Kaplan-Meier method, and Cox proportional hazards models to analyze time-to-event outcomes (acute rejection, graft failure, and death). For allograft immunohistopathology outcomes, we will first develop a comprehensive immune profile of each participant by longitudinal analysis of frequency of T and B cell subsets and function. We will examine how these correlate with immunohistopathology and alloantibody production using Pearson or Spearman correlations. We will compare correlation coefficients between the two experimental groups using Z -tests to determine the distinct effects of each treatment arm. We will also compare the trajectory changes in cell populations and antibody production over 3 and 12 months using both repeated measures ANOVA and random mixed effect models. All tests will be

*Northwestern University Feinberg School of Medicine:* Extended-Release Tacrolimus Vs. Twice-Daily Tacrolimus

two-sided, and an error rate of  $\alpha <0.05$  will be considered statistically significant. All data analyses will be performed using SAS 9.2 statistical software (SAS Inc., Cary, NC).

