## **INCLUSION AND EXCLUSION CRITERIA:**

The target population is adult recipients of immediately functioning living and deceased donor renal allografts. Immediate function will be defined as the absence of the need for hemodialysis in the first week following renal transplantation.

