## **STUDY ENDPOINTS:**

### **Primary endpoints:**

One of the 2 primary end points Kidney transplant function assessed as kidney injury markers in urine samples collected at 12-hour and 24-hour trough levels and 2-hour peak levels at 2nd week, 3rd month, 12th month post transplantation, and at any for-cause biopsy event. The injury markers will be assessed using Myriad-RBM KidneyMAP panel <https://myriadrbm.com/products-services/humanmap-services/kidneymap/>.

The other primary end point is immune activation assessed through serial flow cytometric immunophenotyping for immune cells including T and B cell subpopulations as well as donor-reactive TCR repertoire analysis in biopsy, blood and urine.

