## **PROCEDURES INVOLVED:**

### **Study Design:**

**Donors:** Blood samples (50ml) from donor subjects will be obtained before transplantation. These donor leukocytes will be used as stimulator cells in studies of functional activity of recipient T-cells. These samples will be processed in the research laboratory of co-investigator, [name].

**Renal Transplant Recipients:** All recipients will receive the same induction immunotherapy at the time of transplant.

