**Blood Immunophenotyping.**

The approach will be to conduct a multi-parameter flow cytometric immunophenotyping of peripheral blood before and at 3 and 12 months post-transplant to analyze cellular changes.

Methods (14-16): Our well-established 5-color flow cytometric analyses is performed using whole blood to delineate the cellular makeup in terms of both percentages and absolute numbers (**Table 1**). RBCs are lysed before flow acquisition. The analysis is for defining the T cell subsets, monocytes and natural killer cells (Tube 2), the B cells

including naïve, transitional, memory and effector-memory subsets (Tube 3) and the dendritic cells including immature, monocyteoid and plasmacytoid fractions (Tube 4).

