## Northwestern University Feinberg School of Medicine: Extended-Release Tacrolimus Vs. Twice-Daily Tacrolimus

color-coded microspheres, each coated with a unique HLA antigen has become the main multiplex assay used for the detection of allo-specific antibodies against donor antigens. Its multiplexing power enables the analysis of the antibodies directed to all available synthetic HLA class I and class II alleles in one assay. Utilizing these single antigen HLA beads (SAB) Degauque et al. described a novel assay to identify HLA-specific B cells in transplant recipients (22). We have further developed this novel multiplex bead-based assay to identify HSB (schematically described in **Figures 5 and 6**), and propose here to study the circulating HSB in kidney transplant recipients with chronic AMR.

*Figure 5: Assay Design*

Proposed studies:

1. Frequency of Donor-specific B cells (DSB) by Novel HLA Bead Multiplex Assay: We will analyze the serial samples of peripheral blood mononuclear cells (PBMC) using our novel HLA-bead multiplex assay to identify and determine the changes in frequency of total B, HLA-specific B (HSB) and DSB cells in KT recipients with cAMR in each study arm.

*Figure 6: Analysis Strategy*

2. Immunophenotyping of HLA-specific B cells and Donor-Specific B cells by Flow Cytometry: We will analyze serial samples of PBMC, before and at 3 and 12 months post-transplant, using multi-parameter flow-cytometry for immunophenotyping of (i) total B, HSB and DSB cells with surface expression of IgD, CD24, CD27 and CD38.

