**Sample size and power:**

This proposal bases its sample size calculations on published data demonstrating increased peaks and troughs with conventional tacrolimus and absence of such peaks and troughs with LCP-Tacro/Envarsus® XR (1) and correlation with high doses and nephrotoxicity with conventional tacrolimus (4). Using a two-tailed  $\alpha$  of 0.05, the anticipated effect sizes corresponding to each specific aim between the two treatment arms were calculated using a minimum of 80% statistical power and assumed 10% attrition at 12 months.

For the sample size of  $n= 25$  in each group, the proposed study will have a power of 0.82 and 0.99 to detect effect size of 1.0 and 2.0 for graft function and immune activation (in terms of T cell clonal repertoire change), respectively, between the two treatment arms. Because this is a pilot study, we do not consider the statistical power of secondary outcomes; It is anticipated that a much larger sample size will be needed in order to achieve statistical power for the secondary endpoints in this proposed study.

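### Covariates for the primary analysis are chosen by observed baseline imbalance; for the flow-cytometric T- and B-cell subsets, the planned pre-transplant value should be a pre-specified covariate

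*Combined protocol and SAP*

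**What the plan says.** The primary-objective paragraph of Statistical analysis says that if, in spite of randomisation, "distributions of subjects' baseline characteristics are found to be different between the two experimental groups, these variables will be entered as covariates". This is the only covariate rule in the document. The same section describes preliminary testing of all variables ("We will evaluate continuous variables using t-tests or F-tests and categorical variables using" a chi-square test) and a two-sided 0.05 level, but ties neither to the covariate rule.

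Under Primary endpoints, one of the two primary endpoints is "immune activation assessed through serial flow cytometric immunophenotyping for immune cells including T and B cell subpopulations", together with donor-reactive TCR repertoire analysis. Statistical analysis also lists T- and B-cell subpopulations as primary. Blood Immunophenotyping plans "multi-parameter flow cytometric immunophenotyping of peripheral blood before and at 3 and 12 months post-transplant" and gives the aim as analysing cellular changes. It does not say how the pre-transplant value enters the comparison between arms.

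The other primary measures differ. Urine injury markers are first collected at week 2 (Kidney transplant function). For donor-reactive clone frequency after transplant, the pre-transplant step identifies the clones to be tracked; no pre-transplant value of the same measure is described. The target population is "adult recipients of immediately functioning living and deceased donor renal allografts", so donor source varies and is known for each patient.

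**The concern.** Under randomisation, an observed baseline difference is chance. Whether a variable happens to be imbalanced says nothing about whether it predicts the outcome, and prediction is what makes adjustment worthwhile. A rule triggered by imbalance therefore leaves a predictive variable out of most trials and keeps its variance in the error term. With no candidate list or threshold, it also leaves the content of the primary model to be settled after the data are seen.

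The flow subsets are where this matters most, because a baseline of the same measure is already planned. If that value predicts the month 3 and month 12 values, an imbalance rule will usually waste it. What is at stake is the width of the confidence interval for the arm difference in a 50-patient pilot.

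**Working it through.** **Inputs from the documents.** 25 per arm (Number of Participants); two-sided 0.05; 10% attrition at 12 months, so 25 × 0.9 = 22.5, taken as 22 per arm; power 0.82 and 0.99 for "effect size of 1.0 and 2.0 for graft function and immune activation (in terms of T cell clonal repertoire change" (Sample size and power). No effect size is given for the flow subsets.

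**Assumptions.** Pre/post correlation ρ from 0 to 0.7. The low end must be included because "All recipients will receive the same induction immunotherapy at the time of transplant", so alemtuzumab is given between the pre-transplant and month 3 samples. Two readings of a difference in baseline distributions: a t-test at p<0.05, or a standardised difference above 0.25.

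**The plan's own figures.** Noncentral t, noncentrality d/√(2/n). At d = 1.0 and 25 per arm, 1/0.283 = 3.54 on 48 df gives 0.934; at 22 per arm it gives 0.900. The stated 0.82 does not reproduce from the stated inputs. At d = 2.0 power exceeds 0.999, consistent with the stated 0.99. The mismatch is a separate matter, and this point does not rest on it.

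**How often the rule acts.**
- With p<0.05 at 25 per arm, the arms must differ by 2.011 × √(2/25) = 0.57 SD. Any one variable enters about 5% of the time.
- With 5, 10 or 20 independent variables, the chance that at least one is flagged is 1 − 0.95^k = 23%, 40% or 64%.
- With a standardised difference above 0.25, a variable enters in about 38% of trials at 25 per arm and 41% at 22.

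**Precision.** The unadjusted standard error is SD × √(2/n) = 0.283 SD at 25 per arm. Adjustment multiplies it by √(1 − ρ²), less a small cost for the lost degree of freedom. Simulation with 40,000 trials per cell, p<0.05 trigger, 25 per arm:

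| ρ | Mean SE, rule | Mean SE, always adjusted | Ratio | CI narrower by |
|---|---|---|---|---|
| 0.3 | 0.282 | 0.271 | 0.961 | about 4% |
| 0.5 | 0.281 | 0.246 | 0.875 | about 12% |
| 0.7 | 0.278 | 0.203 | 0.730 | about 27% |

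At ρ of 0 to 0.2 the widths agree to within about 1%, and adjustment is very slightly worse at ρ = 0. The percentages are the same at 22 per arm.

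**Power at 1.0 SD, 22 per arm** (the plan's smaller effect size, borrowed for the subsets):

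| ρ | Rule, p<0.05 | Always | Change in points |
|---|---|---|---|
| 0 | 0.897 | 0.892 | −0.5 |
| 0.1 | 0.898 | 0.895 | −0.3 |
| 0.2 | 0.898 | 0.903 | +0.5 |
| 0.3 | 0.903 | 0.919 | +1.6 |
| 0.5 | 0.909 | 0.959 | +5.0 |
| 0.7 | 0.914 | 0.994 | +8.0 |

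With the 0.25 trigger, the rule gives 0.911, 0.932 and 0.964 at ρ = 0.3, 0.5 and 0.7, against 0.920, 0.956 and 0.994: a gain of 1 to 3 points, with intervals about 2 to 3%, 8% and 19% narrower. If months 3 and 12 are averaged (assumed correlation 0.5 to 0.7 between them), the gain under p<0.05 is 1 to 5 points for ρ of 0.3 to 0.7. At 2.0 SD, power exceeds 0.999 either way.

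**Type I error.** Under the p<0.05 trigger the rule gives about 0.036 to 0.052, falling as ρ rises. Always adjusting gives about 0.05.

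**If the plan means change from baseline.** The variance factor is 2(1 − ρ) = 1.40, 1.00, 0.60 at ρ = 0.3, 0.5, 0.7, against 1 − ρ² = 0.91, 0.75, 0.51 for covariate adjustment. Intervals would be 1 − √(0.91/1.40) = 19%, 1 − √(0.75/1.00) = 13% and 1 − √(0.51/0.60) = 8% narrower, before the degree-of-freedom cost.

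**Donor source, for urine markers and clone frequency.** Assumed 50:50 mix, 22 per arm, 1.0 SD treatment effect. For donor effects of 0.3, 0.5, 1.0 and 1.5 SD, rule against always: 0.899 v 0.900, 0.900 v 0.911, 0.907 v 0.948, 0.909 v 0.979.

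**The case against.** The strongest case on the other side has four parts.

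- **The plan does not say that nothing else may enter.** True. It is silent on prognostic covariates and does not exclude them. But silence leaves the primary model open, and the one rule stated is the imbalance rule.
- **The longitudinal models may already use the pre-transplant value.** The primary-objective paragraph discusses covariance structures, and repeated-measures ANOVA and mixed models are planned for cell-population trajectories. Those models, however, sit in the secondary-endpoint paragraph, refer to 3 and 12 months, and do not mention the pre-transplant value. The text does not settle this. If the value is used as a change score or time point, the size of the gain differs, as shown above.
- **The gain may be nil.** This stands in part. After lymphocyte-depleting induction the correlation may be low, and at 0 to 0.2 there is nothing to gain. A looser reading of the trigger also shrinks the benefit.
- **The benefit falls on a less developed component.** The primary hypothesis names graft function and donor-reactive clones, and the power statement covers only those. Even so, the flow subsets are named as primary in two sections.

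A reader might also infer that choosing covariates by imbalance inflates false positives. As modelled, it does not; the rule is at or slightly below the nominal level. A reader might infer that donor source must be a covariate. No section shows that it predicts any primary measure, so that is clinical judgement and an optional choice.

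**Conclusion.** The concern holds as a loss of precision and an unfixed primary model, chiefly for the flow-cytometric T- and B-cell subsets. It does not show bias or an invalid test.

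Under a p<0.05 trigger, at 22 per arm and 1.0 SD, always adjusting changes power by about −1 to +1 point at correlations 0 to 0.2 and by +2 to +8 points at 0.3 to 0.7. Under a standardised-difference trigger of 0.25, the gain at 0.3 to 0.7 is about 1 to 3 points. It would be wrong to quote the 12% or 27% narrower interval as the expected benefit: those figures need correlations of 0.5 or 0.7, which the documents do not support, and the stricter trigger.

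The recommendation rests on asymmetry. An uninformative covariate costs about one power point; an informative one can give back considerably more. For urine markers and clone frequency, fixing donor source in advance is worth 0 to 1 point for small assumed donor effects and 4 to 7 points only for effects of 1.0 to 1.5 SD.

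**What to change.** Replace the conditional sentence in Statistical analysis with wording such as:

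> Primary models for flow-cytometric T- and B-cell subsets include the pre-transplant value of the same measure, irrespective of observed balance; adjustment for other variables found imbalanced is a sensitivity analysis.

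State also that the pre-transplant value enters as a covariate, so that it is not left open whether a change score or an extra time point is meant.

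Donor source (living or deceased) may be added as a fixed covariate if the investigators judge it prognostic, provided this is decided before the data are seen. HLA-specific and donor-specific B cells should stay out of this sentence: they are not a named primary endpoint, and their frequency assay is described for "HLA-specific B (HSB) and DSB cells in KT recipients with cAMR in each study arm".

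The cost is one SAP sentence and one degree of freedom, or two with donor source. If the covariates carry no information, power at 1.0 SD falls from 0.933 to 0.927 (one) or 0.922 (both) at 25 per arm, and from 0.899 to 0.893 or 0.885 at 22 per arm. No new sample or visit is needed.

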## **NUMBER OF PARTICIPANTS:**

Prospective randomized single center open label study of 2 groups of kidney transplant patients

- Group 1 : standard of care (SOC) control group will receive tacrolimus twice-daily (n=25)
- Group 2 : LCP-Tacro/Envirox® XR group will receive LCPT tablets once daily (n=25)

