## **STUDY TIMELINES:**

We expect the total duration for this study not to exceed 2 years from the date of the last subject's enrollment. Each individual subject will be part of the study for 12 months after transplantation.

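### Ordinary logistic and Cox models are planned for rejection, graft failure and death with 25 patients per arm and no sparse-event method; at 12-month rates of about 5% or less, the odds or hazard ratio may well have no finite value.

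*Combined protocol and SAP*

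**What the plan says.** The Statistical analysis section lists among the secondary endpoints the "incidence of acute rejection, graft loss, and death at 3 and 12 months post kidney transplant". For their analysis it states "we will use logistic regression, Kaplan-Meier method, and Cox proportional hazards models to analyze time-to-event outcomes (acute rejection, graft failure, and death"). It does not say which of the three methods leads for which outcome or time point. The only other method it names for categorical variables is chi-square, and frequencies appear among the preliminary descriptive statistics.

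The Number of participants section sets the arms: "standard of care (SOC) control group will receive tacrolimus twice-daily (n=25") and "group will receive LCPT tablets once daily (n=25"). On follow-up, Study timelines says "Each individual subject will be part of the study for 12 months after transplantation". The Sample size section "assumed 10% attrition at 12 months", calls the study a pilot, and says of the secondary endpoints that "we do not consider the statistical power of secondary outcomes".

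If baseline characteristics differ between the arms, "these variables will be entered as covariates in the statistical analysis". No limit is put on how many.

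No rate or expected count of rejection, graft loss or death is given anywhere. No exact, penalised or other sparse-data method is named.

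**The concern.** Maximum-likelihood logistic and Cox models need events in both arms to give a finite treatment effect. When one arm has none, the likelihood keeps rising as the log odds ratio or log hazard ratio moves towards plus or minus infinity. Software then reports non-convergence or an arbitrary large number with a huge standard error. When neither arm has an event, nothing can be estimated.

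With 25 per arm and 12 months of follow-up this is a practical possibility. The eligibility criteria remove several immunological risk factors: prior transplant, PRA above 40%, donor-specific antibody, positive flow crossmatch and delayed graft function.

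At stake is the usefulness of the clinical outcome results. If the named model fails for an outcome and the plan is silent, the analyst has to choose a replacement after seeing the data. A pilot should pass on event counts and an interval for the risk difference, and the plan does not commit to the latter.

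**Working it through.** **Inputs.** n = 25 per arm (Number of participants). Attrition of 10% at 12 months leaves 25 × 0.9 = 22.5, so 22 to 23 per arm (Sample size and power). The plan states no figure for these outcomes that could be reproduced; its power figures concern the primary endpoints and do not enter here. The event rate p is **assumed**, from 1% to 15% per arm by 12 months.

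**Step 1: does the estimate fail?** Ordinary models were fitted to 0/25 versus 2/25. The logistic fit did not converge (log odds ratio about -29, standard error about 1.6 million). The Cox log hazard ratio was about -25.5 (standard error about 240,000). Neither is an estimate.

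**Step 2: how often would an arm be empty?** With the same rate p in both arms:

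- P(no events in one arm) = (1 - p)^25
- P(at least one arm has none) = 1 - [1 - (1 - p)^25]²
- P(neither arm has any) = (1 - p)^50
- Expected events in total = 50p

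For p = 5%: 0.95^25 = 0.277, so 1 - 0.723² = 0.48, and 0.95^50 = 0.08.

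| Assumed rate per arm | At least one arm with none | Neither arm has any | Expected events, both arms |
|---|---|---|---|
| 1% | 0.95 | 0.605 | 0.5 |
| 2% | 0.84 | 0.36 | 1.0 |
| 4% | 0.59 | 0.13 | 2.0 |
| 5% | 0.48 | 0.08 | 2.5 |
| 10% | 0.14 | 0.005 | 5.0 |
| 15% | 0.03 | under 0.001 | 7.5 |

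The chance of an empty arm passes one half when the common rate is below about 4.8%. With 22 per arm the second column becomes 0.87 at 2%, 0.54 at 5%, 0.19 at 10% and 0.055 at 15%.

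**Step 3: unequal rates.** If the once-daily arm had half the control rate, for example 10% versus 5%, then 1 - (1 - 0.90^25)(1 - 0.95^25) = 1 - 0.928 × 0.723 = 0.33. At 15% versus 7.5% it is 0.16.

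**Step 4: rejection at moderate rates.** At 10% per arm, P(two or fewer events in an arm) is 0.537, so P(at least one arm has two or fewer) = 1 - 0.463² = 0.79. An arm-only model will usually fit but be very imprecise. Five to 7.5 events in total cannot support added covariates. Chi-square is doubtful too: expected events per arm are 25p, which is below 5 for any rate under 20%.

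**Step 5: does the alternative work where the models fail?** Take 2/25 versus 0/25. The Wilson limits are 0.022 to 0.250 and 0 to 0.133. The Newcombe interval for the difference of 0.08 is 0.08 - √(0.058² + 0.133²) = -0.065 to 0.08 + √(0.170² + 0²) = 0.250, that is, -6.5 to +25.0 percentage points. Fisher's two-sided p is 2 × 300/1225 = 0.49. Both are finite and reportable.

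**The case against.** The strongest reply is that the size rests wholly on assumed rates, and that not every feature of the trial points to few events. Deceased-donor grafts are included, donors may be up to 65, there is no maintenance prednisone, and biopsies at months 3 and 12 can detect rejection without symptoms. This stands. A reader might infer that an empty arm is likely for all three outcomes alike. The documents do not support that: at 10% or more under equal rates it is unlikely for rejection.

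A reader might also infer that these models fail whenever events are few, or that they should be deleted. That goes too far. A result such as 3/25 versus 1/25 has a finite odds ratio (3 × 24)/(1 × 22) = 3.3 and a finite Cox estimate, each with a very wide interval. Log-rank, score and likelihood-ratio tests can still be computed when only one arm has events.

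Parts of a sound analysis are already planned: frequencies and Kaplan-Meier curves, which are estimable with no events. Incidence at fixed months also suits logistic regression, so its listing beside time-to-event methods may be only compressed wording. The covariate sentence sits in the paragraph on the primary objective, so applying it to these models is an inference.

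Finally, the study is a pilot that disclaims power for secondary outcomes. That lowers the consequence, since no confirmatory conclusion depends on these models. It does not answer the point, because low power and the absence of a finite estimate are different problems.

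**Conclusion.** The concern holds in a limited form. For graft failure and death, and for rejection if its rate is about 5% or lower, the chance that an arm of 25 has no events runs from about one half (0.48 at 5%) to 0.95 (at 1%). The planned ordinary odds or hazard ratio then has no finite value, and the plan names no substitute. For rejection at 10% to 15% the problem is imprecision and too few events for covariates, not a missing estimate.

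That an empty arm leaves no finite ratio is certain. How often it would happen rests on assumed rates, equal between arms except where stated, and on 25 patients observed per arm; attrition makes it somewhat worse.

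**What to change.** Rewrite the sentence on the secondary event outcomes in the Statistical analysis section as follows:

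- **Lead analysis.** For each of acute rejection, graft loss and death, report the number of patients with the event by arm by months 3 and 12. Add the Kaplan-Meier cumulative incidence and its between-arm difference with 95% CI, which allows for the assumed 10% attrition.
- **Complete follow-up, or an arm with no events.** Give the risk difference with a Newcombe or exact 95% CI and state the denominator. This is needed because the usual Kaplan-Meier variance is zero in an arm without events.
- **Test.** Name one exact test, such as Fisher, in place of chi-square.
- **Models.** Keep any logistic or Cox model as supportive only, with treatment arm as the sole term, Firth-penalised, with profile-likelihood intervals. State that the baseline-covariate rule does not apply to these outcomes.

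The change is to SAP wording only; no visits, samples or patients are added. The costs are that no covariate-adjusted ratio will be reported for these outcomes, and that exact methods are somewhat conservative.

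### An unlisted set of between-arm Z-tests on correlations, each judged at 0.05, is to be read as showing treatment-arm effects, with no multiplicity control or exploratory label

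*Combined protocol and SAP*

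**What the plan says.** All of this is in the combined protocol and SAP.

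- **Statistical analysis, secondary endpoints.** An immune profile is built for each participant by "longitudinal analysis of frequency of T and B cell subsets and function". The next step reads: "We will examine how these correlate with immunohistopathology and alloantibody production using Pearson or Spearman correlations". Then comes the between-arm step: "We will compare correlation coefficients between the two experimental groups using Z -tests to determine the distinct effects of each treatment arm".
- **Same section, closing sentences.** One rule covers all tests: two-sided, with an error rate below 0.05 that "will be considered statistically significant". No adjustment is mentioned.
- **Blood Immunophenotyping.** The whole-blood panel is used "to delineate the cellular makeup in terms of both percentages and absolute numbers", so each subset may be available on two scales.
- **Secondary endpoints and Statistical analysis.** Histology and donor-specific antibody are both assessed at months 3 and 12.
- **Sample size and power.** The only caveat on secondary outcomes is: "Because this is a pilot study, we do not consider the statistical power of secondary outcomes". The text adds that a much larger sample would be needed for them.

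No section lists the correlations to be compared, gives their number, names a leading pair, visit or type of coefficient, or calls these tests exploratory.

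**The concern.** The Z-test sentence does more than describe data. It gives the tests the purpose of establishing what each treatment does, and the 0.05 rule applies to each test separately. When the list of tests is open, chance alone will often produce some significant differences. The plan as written allows any of them to be reported as an effect of the once-daily formulation or of standard tacrolimus. A reader of the results could not tell how many comparisons lay behind a reported one. Low power adds to the problem, because a single positive from a weak test says little about a true difference.

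**Working it through.** The plan states no test count and no family-wise error rate, so there is no figure of its own to reproduce on this point. The check counts plausible families and calculates the chance of at least one false positive in each.

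**Inputs**
- Alpha: 0.05 two-sided per test (Statistical analysis).
- Patients: 25 per arm with 10% attrition at 12 months (Sample size and power). 25 × 0.9 = 22.5, taken as 22.
- Outcomes: 2, counting immunohistopathology and alloantibody as one score each. This is the minimum.
- Visits: months 3 and 12. Testing at each visit is an assumption based on when the outcomes are measured; the Z-test sentence names no visit.
- Cell measures: the analysis text limits the profile to T and B cells. Table 1 carries CD4 and CD8, and Blood Immunophenotyping names four B-cell subsets (naïve, transitional, memory, effector-memory), which makes 6. The text introducing Table 2 adds activated, effector, memory, anergic and exhausted fractions and regulatory T and B cells, 7 more, which makes 13. Monocytes, NK cells and dendritic cells are left out because they are neither T nor B cells.

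**Number of tests**
- Narrow, one visit: 6 × 2 × 1 = 12
- Narrow, both visits: 6 × 2 × 2 = 24
- All named T and B fractions, both visits: 13 × 2 × 2 = 52

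These counts use one scale only and leave out cell function and the HLA-specific and donor-specific B-cell phenotypes.

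**Family-wise error if the tests were independent:** 1 − 0.95^k
- k = 12: 1 − 0.95^12 = 0.46
- k = 24: 1 − 0.95^24 = 0.71
- k = 52: 1 − 0.95^52 = 0.93

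This passes one half at k = 14 (0.51; k = 13 gives 0.49).

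**Allowing for dependence.** Subsets and visits are correlated within a patient, which lowers these figures. Fisher Z-tests were simulated with 22 per arm and no arm difference. Correlation between subsets ran from 0 to 0.7, and correlation between visits from 0 to 0.8.

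| Tests | Chance of at least one false positive | Expected false positives (k × 0.05) |
|---|---|---|
| 12 | about 0.3 to 0.46 | 0.6 |
| 24 | about 0.46 to 0.69 | 1.2 |
| 52 | about 0.6 to 0.93 | 2.6 |

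The low end of each range is the strongest dependence tried.

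**Power of one Z-test at 22 per arm**
- Standard error of the difference in Fisher z: √(2/(22 − 3)) = 0.324.
- r = 0 versus r = 0.5: atanh(0.5) = 0.549, and 0.549/0.324 = 1.69. Power is Φ(1.69 − 1.96) = about 0.39.
- For 80% power the difference must be (1.96 + 0.84) × 0.324 = 0.909, that is r = 0 versus tanh(0.909) = 0.72.

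**The case against.** The strongest reply has four parts.

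1. **These are secondary, mechanistic analyses in a 50-patient pilot.** The plan itself says they are underpowered, and formal error control for such work is partly a matter of preference. This stands as a reason to keep the point minor. It does not answer it: the caveat concerns missed effects, while the 0.05 rule and the stated purpose of the Z-tests remain in force.

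2. **The number of tests is not fixed.** The longitudinal profile could reduce to one summary per subset, and the Z-test sentence does not say that every coefficient at every visit is compared. This is correct, and it is why the result is given as a range.

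3. **A reader might infer that a false positive is more likely than not, or nearly certain, and that any reported differences would be mostly chance.** The documents do not support this. The 12-test family stays below one half throughout, and the 24-test family falls to about 0.46 under strong dependence. Saying that most findings would be false needs a prior share of true null differences, which the plan does not give.

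4. **A reader might also infer that Pearson tests on skewed cell counts would inflate each test's error.** The Statistical analysis section plans to examine distributions and transform where necessary, so that charge is not made here. The choice between Pearson and Spearman does remain open.

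**Conclusion.** The point holds, as a minor one. The plan applies an unadjusted 0.05 to an unlisted set of between-arm correlation tests and assigns the results to the treatment arms. The false-positive chance ranges from about 0.3 (12 tests, strong dependence) to about 0.93 (52 tests, close to independence), so even the lowest figure is about six times 0.05.

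The range rests on no true arm difference in any correlation, 22 patients per arm, one score per outcome, and a test count inferred from the panels and visit schedule. It does not show that any particular finding would be false. It shows that a single significant Z-test could not support the reading that the plan gives it.

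**What to change.** In the secondary-endpoint paragraph of Statistical analysis:

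1. Delete the closing clause of the Z-test sentence, which gives the tests the purpose of establishing what each arm does.
2. Label the correlation analyses and the between-arm Z-tests exploratory.
3. Report every coefficient computed, with a 95% confidence interval for each between-arm difference.
4. If any p-value is to be called significant, apply a Benjamini-Hochberg adjustment across the full list of tests run, and publish that list. This controls the false discovery rate, not the family-wise rate calculated above; for exploratory work that is a reasonable target.

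The change is to wording only and needs no added patients, samples or assays. The cost is that isolated correlation differences with p < 0.05 can no longer be reported as treatment effects.
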